**1.7.1 The role of EphB4 and ephrinB2 in mCRPC and correlation with outcomes**

Mechanistically, sEphB4-HSA acts by binding to Ephrin B2 and preventing it's binding to EphB4. Therefore it is important to evaluate the expression of both binding partners and correlate response to therapy if activity of the drug is seen.

**1.7.2 The role of molecular biomarkers (PI3K pathway, P53, and MYC expression) and their correlation with clinical response of sEphB4.**

Our preliminary in vitro and in vivo studies have identified a relationship between PTEN/PI3K, Myc and p53 pathway to EphB4 expression and the response to EphB4 target therapy. Proposed correlation studies are geared towards understanding the various genomic alterations that can predict efficacy of sEphB4. To this end, we will perform IHC on available tissue for EPHB4, EFNB2, AR, PTEN, p-AKT, and MYC and analyze genomic alterations that are described in the results of molecular analysis reports from standard of care tests (i.e., results from standard of care NGS testing/genetic testing/ genomic testing, etc.). We will also utilize cfDNA results to analyze the changes in the alteration level at baseline and after treatment.

**NU Study Number:** NU 18U10

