**3.2 Exclusion Criteria**

3.2.1 Patients who have received more than 3 prior treatment therapies (life prolonging) for mCRPC are not eligible.

3.2.2 Patients who have had radiotherapy  $\leq 14$  days prior to entering the study are not eligible.

*Note: Palliative radiation therapy is allowed.*

3.2.3 Patients who have had systemic therapy for prostate cancer  $\leq 21$  days or 5-half lives (whichever is shorter) are not eligible.

*Note: Patients can receive a stable dose of bisphosphonates for bone metastases, including zoledronic acid, or denosumab before and during the study as deemed appropriate by the treating physician. Patients must continue Androgen Deprivation Therapy.*

3.2.4 Patients receiving any other investigational agents are not eligible.

3.2.5 Patients with Small cell carcinoma of the prostate are not eligible.

*Note: Neuroendocrine differentiation is permitted. If there is doubt about this and it is clinically indicated then a biopsy should be obtained to document histological differentiation.*

3.2.6 Patients who have a history of allergic reactions attributed to compounds of similar chemical or biologic composition to sEphB4-HSA are not eligible.

AND

Patients who have had prior exposure to compounds of similar chemical or biologic composition to sEphB4-HSA are not eligible.

3.2.7 Patients who have an uncontrolled intercurrent illness including, but not limited to any of the following, are not eligible:

- Ongoing or active infection requiring systemic treatment
- Symptomatic congestive heart failure (New York Heart Association Class III or IV congestive heart failure)
- Unstable angina pectoris
- Serious cardiac arrhythmia

3.2.8 Patients with uncontrolled hypertension (defined as systolic BP  $\geq 160$  mmHg or diastolic BP  $\geq 95$  mmHg) are not eligible.

*Note: Patients with a history of hypertension are allowed provided blood pressure is controlled by anti-hypertensive treatment*

3.2.9 Patients with Electrocardiogram (ECG) with QT interval (QTc)  $> 480$  msec are not eligible.

3.2.10 Patients with other malignancy that has progressed or has required active systemic treatment in the last 3 years.

**NU Study Number:** NU 18U10

*Note: Patients with basal cell carcinoma of the skin, squamous cell carcinoma of the skin that has undergone potentially curative therapy or carcinoma in situ or non-muscle invasive bladder cancer are not excluded.*

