## 5 STUDY PROCEDURES

Time Period	Screening (≤1 month unless otherwise indicated) 	On Treatment (1 Cycle = 14 Days)							Off Treatment	
		Cycle 1	Cycle 2	Cycle 3	Cycle 4	Cycle 5	Cycle 6	Cycle 7+ 	End of Treatment 	Follow -up 
Baseline	Week 1 Day 1	Week 3 Day 1	Week 5 Day 1	Week 7 Day 1	Week 9 Day 1	Week 11 Day 1	Week 13 Day 1			
Assessment or Activity										
Informed Consent	X									
Medical history 	X 								X 	
Physical exam 	X	X	X	X	X	X	X		X	
ECOG status	X	X	X	X	X	X	X		X	
Toxicity assessment		X	X	X	X	X	X		X	
Review Concomitant Medications	X	X		X		X			X	
Tumor Imaging 	X				X 				X	
CBC + diff, chemistry, liver enzymes *3, 4	X	X	X	X	X	X	X		X	
PSA *5	X	X		X		X			X	
EKG *6	X			X	As clinically indicated				As Clinically Indicated	
Research blood 	X					X			X	
Archival tissue sample 				X					X	
sEphB4-HSA administration 		X	X	X	X	X	X			
Survival Status										X

\*Can be completed  $\pm 3$  days of drug administration

- Includes vital signs (pulse, blood pressure) and height (baseline only) and weight.
- Bone scan, CXR or CT of chest, CT or MRI or abdomen and pelvis; with IV contrast if renal function adequate; the same modality used at baseline should be used throughout as clinically indicated. Imaging will occur at baseline and 2 months ( $\pm 7$  days) after starting therapy; thereafter, imaging will be conducted every 3 months ( $\pm 7$  days). After 1 year, imaging can be done every 4 months ( $\pm 7$  days) for patients with stable disease or better. Scans may also be conducted at any time, if clinically indicated.
- Study labs include: CBC with diff, alkaline phosphatase, albumin, total bilirubin, BUN, creatinine, calcium, glucose, AST, ALT, and electrolytes. These study safety labs are to be conducted within  $\leq 2$  weeks prior to registration.
- Testosterone level only at baseline.
- Assessment of response to therapy with PSA will occur on day 1 of odd cycles.
- Required for all patients at baseline and C3D1. Then only as clinically indicated thereafter.
- Blood will be collected at baseline, cycle 5 day 1, and at end of treatment for additional molecular analysis (see section 9).

**NU Study Number:** NU 18U10

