8. Permission to obtain archival tissue samples of primary lesion and metastatic lesion sites will be obtained at baseline. The samples themselves will be collected only if available and only when requested by the Principal Investigator or Principal Investigator's designee; they may be collected at any time during the study, per PI request. Refer to the lab manual for details.
9. If there is concern about transformation to small cell cancer histology then a standard of care biopsy may be appropriate given that this is an exclusion criteria for this trial.
10. If tumor tissue is biopsied or resected as part of standard medical care or assessment from the time of study enrollment until progression then archival tissue from this biopsy/resection may be used for assay of the markers defined within the protocol to document molecular pathway characteristics and immune cell infiltration at that point to correlate with whether the cancer is responding, stable or progressing.
11. Patients will receive sEphB4-HSA 1000mg IV (60min infusion) on day 1 of each cycle along with continuation of androgen deprivation therapy. Refer to Table 4-2-1 for required premedication regimens.
12. Imaging must be completed and reviewed within 6 days (whenever feasible) prior to receiving treatment.
13. **Please see Table Below.** Beginning at Cycle 7, cycle length will be 21 days and patients will return for treatment on Day 1 of each cycle.
14. Patients will return for an End of Treatment (EOT) visit 30 ( $\pm 3$ ) days of the last dose of study treatment or prior to start of new treatment.
15. If off treatment for reasons other than disease progression, patients will be followed every 6 months, until objective progression or patient starts alternative therapy for a maximum of 1 year.
16. If patient has had molecular testing (i.e., NGS testing, genetic testing, genomic testing, etc.) performed as standard of care prior to study entry or at any time during study participation, collect a copy of the results report for correlative analyses. Refer to Section 9 for details.
17. Screening/baseline assessments are to be conducted within 1 month prior to registration unless otherwise indicated.

## Study Calendar Beginning at Cycle 7

Time Period	On Treatment (1 Cycle = 21 Days)						Off Treatment	
	Cycle 7	Cycle 8	Cycle 9	Cycle 10	Cycle 11	Cycle 12+	End of Treatment 	Follow-up 
	Week 13 Day 1	Week 16 Day 1	Week 19 Day 1	Week 22 Day 1	Week 25 Day 1	Week 28 Day 1		

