#### **9.2 Sample Collection Guidelines**

From each patient, specimens will be collected as below:

- a. If available, archival tissue of primary tumor and metastatic tumor will be obtained.
- b. Blood for cfDNA (pre-treatment, Cycle 3 Day 1 and at clinical progression or when off study, whichever is first)

Please refer to Lab Manual for instructions on sample collection.

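### The screening window lets the baseline cfDNA and cytokine sample be drawn up to a month before registration, so for patients sampled early the change to Cycle 5 Day 1 may mix prior-therapy withdrawal with study-drug effect

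*Combined protocol and SAP*

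**What the plan says.** In the Section 5 calendar, the research blood row is marked under Screening/Baseline, at Cycle 5 and at End of Treatment. The Cycle 1 Day 1 cell is empty. Footnote 7 gives the time points: "Blood will be collected at baseline, cycle 5 day 1, and at end of treatment for additional molecular analysis". Footnote 17 sets the window for the screening column: "Screening/baseline assessments are to be conducted within 1 month prior to registration unless otherwise indicated". Footnote 3 gives a tighter limit of two weeks, but for the safety laboratory tests only.

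Section 4.1 and the Section 9 table also call the first sample simply baseline, and Section 9.2 calls it pre-treatment. None of them gives a day or a window. Section 3 requires registration before treatment starts but sets no maximum interval between the two.

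Exclusion 3.2.3 bars patients whose systemic prostate cancer therapy falls within 21 days or "5-half lives (whichever is shorter) are not eligible". It does not say from which date this is counted. Androgen deprivation continues throughout and is not part of the washout.

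On the use of the samples, Section 1.7.2 says: "We will also utilize cfDNA results to analyze the changes in the alteration level at baseline and after treatment". Objective 2.3.4 concerns changes in circulating immune markers under treatment. Section 10 describes a single-arm study.

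**The concern.** Without a control arm, the within-patient change from baseline is the only evidence the trial can offer that the drug alters circulating markers. That evidence depends on the baseline sample reflecting the patient's state just before the first dose.

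Eligibility requires progression on a second-generation AR-targeted agent (3.1.4), so recent prior therapy is plausible. If blood is drawn early in the screening window, the patient may still be taking that agent or may just have stopped it. The later change then contains up to three components: withdrawal of the old drug, a period of untreated progressive disease, and the study drug. Analysis cannot recover a pre-dose sample that was never drawn. Section 10.2 names no method for the cfDNA or cytokine change and no adjustment for time since prior therapy.

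**Working it through.** **Inputs from the documents**
- Cycles 1 to 6 last 14 days (Sections 4.1 and 4.2).
- Screening window *W*: up to 1 month before registration (Section 5, footnote 17).
- Washout *D*: the shorter of 21 days and 5 half-lives (3.2.3).

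**Assumptions, because the documents do not settle them**
- One month is 30 days (range 28 to 31).
- Washout is counted back from registration.
- The gap *g* from registration to first dose is 0 days, with 7 and 14 as alternatives.
- Where 5 half-lives is the shorter limit, illustrative washouts are 14 days and 5 days (the latter being a half-life of 1 day).

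**Step 1: the plan's own calendar position.** Cycle 5 Day 1 falls 4 × 14 = 56 days after Cycle 1 Day 1, which is 8 full weeks, so Week 9 Day 1. The calendar shows the same.

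**Step 2: window days on which the patient could still be on the previous drug.** Overlap = *W* − *D*.

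| Window *W* | Washout *D* | Overlap | Share of window |
|---|---|---|---|
| 28 | 21 | 7 days | 25% |
| 30 | 21 | 9 days | 30% |
| 31 | 21 | 10 days | 32% |
| 30 | 14 (assumed) | 16 days | 53% |
| 30 | 5 (assumed) | 25 days | 83% |

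A draw later in the window can still fall inside the washout itself. If washout is counted back from first dose instead, the overlap is *W* − *D* + *g*, which is larger whenever dosing follows registration by some days. If it were counted back from the blood draw, the overlap with the old drug would vanish and only the untreated interval in Step 3 would remain.

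**Step 3: longest baseline-to-Cycle 5 Day 1 interval.** Interval = *W* + *g* + 56, of which *W* + *g* days precede the first dose.
- *W* = 30, *g* = 0: 30 + 56 = 86 days, and 30/86 = 35% precede any study drug.
- *W* = 28 or 31, *g* = 0: 84 or 87 days, with 33% or 36% before the first dose.
- *W* = 30, *g* = 7 or 14: 93 or 100 days, with 37/93 = 40% or 44/100 = 44% before the first dose.

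**Step 4: with a pre-infusion draw on Cycle 1 Day 1.** The interval is 56 days, and none of it precedes the first dose. Any washout required before registration is complete when the sample is taken.

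**The case against.** One month is a maximum. The mixing needs a patient who was bled early while on, or just off, prior therapy, and the documents give no share of such patients. A reader might infer that every baseline-to-Cycle 5 change is contaminated. The text supports only that the window permits it. This limit stands.

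The Lab Manual, to which Sections 9.2 and 9.3 refer, is not among the documents and could set a tighter draw time. The pre-treatment wording in 9.2 would be compatible with a Cycle 1 Day 1 draw. That is possible, but the protocol calendar as written places the draw at screening.

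The stakes are low. The objectives are exploratory, Section 10.2 plans descriptive summaries without tests, and its marker analysis is by PSA response status rather than by change over time. PSA has its own Cycle 1 draw, so the primary endpoint and the two-stage decision are untouched. All of this stands and sets the weight of the point. Moving the draw is also only a partial remedy, because the natural course of disease over the 56 days remains confounded with drug effect in a single arm.

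A reader might also infer that the calendar's End of Treatment sample contradicts Sections 4.1 and 9.2. It does not. Section 4.1 allows the last sample at progression or at end of treatment, and 9.2 sets it "at clinical progression or when off study, whichever is first". Footnote 14 lets the End of Treatment visit come before 30 days if new treatment is starting, so no fixed level of residual drug can be attributed to that sample. No passage presents it as either an on-treatment or a washed-out measurement.

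**Conclusion.** The point holds as a permitted scenario. The supplied documents allow a baseline research sample up to a month before registration, which is longer than the longest required washout. Under the stated assumptions, the earliest 9 of 30 window days (7 to 10 for a month of 28 to 31 days) can fall on the previous drug with a 21-day washout. With an assumed 5-day washout this rises to 25 of 30. Up to about 30 of 86 days between baseline and Cycle 5 Day 1 can precede any study drug, and more if dosing follows registration late. For patients sampled early, the change may reflect withdrawal of prior therapy and untreated progression as well as study drug, and the design cannot separate them.

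How many patients this affects is unknown. The size rests on the assumed washout reference date and month length. The consequence is confined to the exploratory circulating-marker analyses. It is worth correcting because the remedy is cheap and the missing sample cannot be recreated later.

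**What to change.** - Move the baseline research blood to Cycle 1 Day 1 and state that it is drawn before the infusion. The ±3-day allowance attached to CBC and PSA should not apply to it.
- Require the Cycle 5 Day 1 cfDNA tube before infusion too. Section 4.1 attaches that condition only to the cytokine sample.
- Make footnote 7 in both calendars, Section 4.1, the Section 9 table and Section 9.2 say the same thing. This includes reconciling the Cycle 3 Day 1 cfDNA draw in 9.2 with Cycle 5 Day 1 everywhere else.
- For any patient already sampled at screening, record the draw date and the date of last prior therapy, so that the interval can be shown beside the marker change.

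Cost: small edits in several places. The number of tubes is unchanged, the patient is already attending a treatment visit, and no tubes are used on screen failures. The one loss is that there would be no research sample from before registration.

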## **6 ENDPOINT ASSESSMENT**

### **6.1 Definitions**

#### **6.1.1 Evaluable patients**

Evaluable for primary endpoint of PSA response. All patients who received at least 1 dose of the study drug and who also had a followup PSA test conducted prior to initiating subsequent therapy will be evaluable for PSA response.

Evaluable for toxicity. All patients who received at least 1 dose of the study drug will be evaluable for toxicity.

Evaluable for objective response. Only those patients who have measurable disease present at baseline will be considered evaluable for objective response. These patients will have their response classified according to the definitions stated below.

Evaluable Non-Target Disease Response. Patients who have lesions present at baseline that are evaluable but do not meet the definitions of measurable disease will be considered evaluable for non-target disease. The response assessment is based on the presence, absence, or unequivocal progression of the lesions.

#### **6.1.2 Disease Parameters by RECIST V1.1**

Measurable disease. Measurable lesions are defined as those that can be accurately measured in at least one dimension (longest diameter to be recorded) as  $\geq 20$  mm by chest x-ray, as  $\geq 10$  mm with CT scan, or  $\geq 10$  mm with CT scan, MRI, or calipers by clinical exam. All tumor measurements must be recorded in millimeters (or decimal fractions of centimeters).

*Note: Tumor lesions that are situated in a previously irradiated area should not be considered measurable unless they have demonstrated progression.*

Malignant lymph nodes. To be considered pathologically enlarged and measurable, a lymph node must be  $>15$  mm in short axis when assessed by CT scan (CT scan slice thickness recommended to be no greater than 5 mm). At baseline and in follow-up, only the short axis will be measured and followed.

Non-measurable disease. All other lesions (or sites of disease), including small lesions (longest diameter  $<10$  mm or pathological lymph nodes with  $\geq 10$  to  $<15$  mm short axis), are considered non-measurable disease. Bone lesions, leptomeningeal disease, ascites, pleural/pericardial effusions, lymphangitis of skin or lung, inflammatory breast disease, and abdominal masses (not followed by CT or MRI), are considered as non-measurable.

*Note: Cystic lesions that meet the criteria for radiographically defined simple cysts*

*should not be considered as malignant lesions (neither measurable nor non-measurable) since they are, by definition, simple cysts.*

*'Cystic lesions' thought to represent cystic metastases can be considered as measurable lesions, if they meet the definition of measurability described above. However, if non-cystic lesions are present in the same patient, these are preferred for selection as target lesions.*

Target lesions. All measurable lesions up to a maximum of 2 lesions per organ and 5 lesions in total, representative of all involved organs, should be identified as target lesions and recorded and measured at baseline. Target lesions should be selected on the basis of their size (lesions with the longest diameter), be representative of all involved organs, but in addition should be those that lend themselves to reproducible repeated measurements. It may be the case that, on occasion, the largest lesion does not lend itself to reproducible measurement in which circumstance the next largest lesion which can be measured reproducibly should be selected. A sum of the diameters (longest for non-nodal lesions, short axis for nodal lesions) for all target lesions will be calculated and reported as the baseline sum diameters. If lymph nodes are to be included in the sum, then only the short axis is added into the sum. The baseline sum diameters will be used as reference to further characterize any objective tumor regression in the measurable dimension of the disease.

Non-target lesions. All other lesions (or sites of disease) including any measurable lesions over and above the 5 target lesions should be identified as non-target lesions and should also be recorded at baseline. Measurements of these lesions are not required, but the presence, absence, or in rare cases unequivocal progression of each should be noted throughout follow-up.

#### 6.1.3 **Methods for Evaluation of Measurable Disease**

All measurements should be taken and recorded in metric notation using a ruler or calipers. All baseline evaluations should be performed as closely as possible to the beginning of treatment and never more than 6 weeks before the beginning of the treatment.

The same method of assessment and the same technique should be used to characterize each identified and reported lesion at baseline and during follow-up. Imaging-based evaluation is preferred to evaluation by clinical examination unless the lesion(s) being followed cannot be imaged but are assessable by clinical exam.

Clinical lesions. Clinical lesions will only be considered measurable when they are superficial (e.g., skin nodules and palpable lymph nodes) and 10 mm diameter as assessed using calipers (e.g., skin nodules). In the case of skin lesions, documentation by color photography, including a ruler to estimate the size of the lesion, is recommended.

Conventional CT and MRI. This guideline has defined measurability of lesions on CT scan based on the assumption that CT slice thickness is 5 mm or less. If CT scans have slice thickness greater than 5 mm, the minimum size for a measurable lesion should be twice the slice thickness. MRI is also acceptable in certain situations (e.g. for body scans).

As with CT, if an MRI is performed, the technical specifications of the scanning sequences used should be optimized for the evaluation of the type and site of disease. Furthermore, as with CT, the modality used at follow-up should be the same as was used at baseline and the lesions should be measured/assessed on the same

pulse sequence. Ideally, the same type of scanner should be used and the image acquisition protocol should be followed as closely as possible to prior scans. Body scans should be performed with breath-hold scanning techniques, if possible.

**6.1.4 Methods of Evaluation of Bone disease:**

Bone disease will be evaluated using technetium Radionuclide bone scan and PCWG3 using PCCTC bone scan forms.

**6.1.5 PSA response criteria:**

These definitions are intended to characterize the PSA changes on study for the purpose of reporting of results.

Complete Response (CR): Undetectable PSA ( $\leq 0.2$  ng/ml) that is confirmed by another PSA level at no less than 4 weeks interval ( $\pm 3$  days).

Partial Response (PR): Decrease in PSA value by  $\geq 50\%$  that is confirmed by another PSA level at no less than 4 weeks interval ( $\pm 3$  days).

Stabilization (SD): Patients who do not meet the criteria for PR or PD for at least 90 days on study will be considered stable

Progression (PD): 25% increase over baseline or nadir whichever is lower and an increase in the absolute value of PSA level by 2 ng/ml that is confirmed by another PSA level at no less than 4 weeks interval.

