Diagnosis & Key Eligibility Criteria	
Inclusion Criteria
 
 
Patients must have pathologically confirmed diagnosis of prostate adenocarcinoma
 
Patients must have metastatic (M1) disease as evidenced by soft tissue and/or bony metastases on CT or MRI scan or technetium bone scan.
 
Patients must have castration resistant disease with disease progression despite castrate levels of testosterone (testosterone < 50 ng/dL)
 
 
Exclusion Criteria
 
 
Patients who have had radiotherapy ≤14 days prior to entering the study are not eligible.
 
Patients who have had systemic therapy for prostate cancer ≤21 days or 5-half lives (whichever is shorter) are not eligible.
 
 
Note: Patients can receive a stable dose of bisphosphonates for bone metastases, including zoledronic acid, or denosumab before and during the study as deemed appropriate by the treating physician.
 
 
Patients receiving any other investigational agents are not eligible.
 
 
See section 3.0 for complete list

Treatment Plan	
sEphB4-HSA will be administered as an IV infusion over 60 minutes on day 1 of each cycle (1 cycle = 14 days) along with continued androgen deprivation therapy (ADT). Beginning at Cycle 7, cycle length will be 21 days and patients will return for treatment on Day 1 of each cycle. Patients may continue to receive sEphB4-HSA treatment until no longer clinically benefiting (PCWG3), unacceptable toxicity, treatment delay ≥4 weeks, or prohibitive illness/change in patient's condition, or patient decides to withdraw from study. Response assessment with PSA will occur on Day 1 of odd cycles (every 28 days). Imaging will occur at baseline and 2 months after starting therapy; thereafter, imaging will be conducted every 3 months. After 1 year, imaging can be done every 4 months for patients with stable disease or better. Scans may also be conducted at any time, if clinically indicated. Once off treatment continue follow-up for 4 weeks or resolution/stabilization of AE ≤ Grade 1. If off treatment before progressive disease, patients will be followed every 6 months, until objective progression or starts alternative therapy for a maximum of 1 year.

NU Study Number: NU 18U10

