## 6.3 Assessment of secondary endpoints

- 6.3.1 The safety and tolerability of sEphB4-HSA in patients with mCRPC will be assessed according to NCI CTCAE v 5.0 and reported by the toxicity, severity, and attribution will be recorded for each cycle.
- 6.3.2 The time to PSA progression will be assessed by calculating the interval from administration of the first dose of drug on cycle 1 day 1 to PSA progression. PSA progression is defined by the criteria in section 6.1.5 PSA will be assessed every odd cycle.
- 6.3.3 The overall response rate will be the proportion of patients with measurable disease who received at least 1 dose of the study drug and as their best response achieved a partial or complete response (responder). A subject will be classified as a responder if the RECIST 1.1 criteria for a CR or PR are satisfied (see 10.1.6 and 10.1.7) as well as the absence of confirmed progression on bone scan assessed by PCWG3 (see 10.1.8) at any time up to and including the defined analysis cut-off point. Disease evaluation will be assessed by imaging at baseline and 2 months after starting therapy; thereafter, imaging will be conducted every 3 months. After 1 year, imaging can be done every 4 months for patients with stable disease or better. Scans may also be conducted at any time, if clinically indicated.

6.3.4 The time to radiologic progression (rPFS) will be assessed by calculating the interval from administration of the first dose of drug on cycle 1 day 1 to the time to radiologic progression by RECIST 1.1 or PCWG3 bone criteria (10.1.6-108) or death from any cause. Imaging will occur at baseline and 2 months after starting therapy; thereafter, imaging will be conducted every 3 months. After 1 year, imaging can be done every 4 months for patients with stable disease or better. Scans may also be conducted at any time, if clinically indicated.

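### PSA progression needs confirmation at 4 weeks or more with no day tolerance, unlike CR and PR, so compliant 28-day draws can fail to confirm it; the usual effect is delay, with event loss confined to the end of treatment

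*Combined protocol and SAP*

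**What the plan says.** - **Confirmation rules (Section 6.1.5).** CR and PR each need a PSA change "that is confirmed by another PSA level at no less than 4 weeks interval ( $\pm 3$ days"). Progression needs a 25% rise over baseline or nadir, whichever is lower, and an absolute increase "by 2 ng/ml that is confirmed by another PSA level at no less than 4 weeks interval". No tolerance follows, and no reason is given for the difference.
- **Endpoint (Section 6.3.2).** For time to PSA progression, "PSA progression is defined by the criteria in section 6.1.5", so this line is the event definition. Section 6.3.2 also puts PSA on every odd cycle.
- **Schedule, Cycles 1-6.** The Study Summary (Treatment Plan) says "Response assessment with PSA will occur on Day 1 of odd cycles (every 28 days"). The PSA row of the Section 5 calendar carries the asterisk footnote "Can be completed $\pm 3$ days of drug administration".
- **Schedule from Cycle 7.** Cycles last 21 days, and the second calendar in Section 5 has PSA on day 1 of each cycle.
- **After treatment.** PSA is marked at EOT. Footnote 14 reads "Patients will return for an End of Treatment (EOT) visit 30" (±3) days from the last dose, or before new treatment starts. The Follow-up column of both calendars marks only survival status.
- **Not stated.** The plan does not say whether progression is dated at the first rise or at its confirmation. Neither Section 6.3.2 nor Section 10.2 gives a censoring rule for this endpoint.

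**The concern.** The nominal spacing of PSA draws in Cycles 1-6 equals the minimum confirmation interval for progression, so nothing is left to absorb the permitted draw window. A patient whose second PSA comes a day early, within the protocol, has a pair that could confirm a response but cannot confirm a progression. From Cycle 7 the nominal spacing is below the minimum.

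The endpoint at stake is time to PSA progression, summarised by Kaplan-Meier with a 90% CI for the median (Section 10.2) in at most 25 evaluable patients. Late or missed confirmation can only push that estimate toward longer times. A patient on study at least 90 days with an unconfirmed rise and no PR would also meet the Section 6.1.5 wording for PSA stabilization.

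**Working it through.** The plan gives no failure rate for confirmation, so there is no figure of its own to reproduce.

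**Inputs**
- Minimum gap for progression: 28 days. For CR and PR: 28 days with ±3, read here as at least 25 days (Section 6.1.5).
- Draw window: ±3 days around dosing (Section 5, asterisk footnote).
- Nominal spacing *s*: 28 days through C7; from Cycle 7, 21 days by the calendar or 42 days by the odd-cycle rule in Section 6.3.2.
- EOT: 30 (±3) days after the last dose (Section 5, footnote 14).
- Dosing day: ±3 days in Cycles 1-6 (Section 8.1.5), used only in the sensitivity and worst-case checks.
- Assumption: each draw offset *d* is uniform on −3, …, +3 and the offsets are independent. The documents give no distribution.

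**Formula.** Gap = *s* + *d2* − *d1*. Of the 7 × 7 = 49 combinations, 7 − *k* have *d2* − *d1* = −*k*, for *k* = 0 to 6; positive differences mirror these.

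**1. 28-day pairs (C1-C3, C3-C5, C5-C7).** The gap runs from 22 to 34 days.
- As written, the pair fails if *d2* − *d1* ≤ −1: (6+5+4+3+2+1)/49 = 21/49 = 42.9%.
- With the tolerance, it fails if *d2* − *d1* ≤ −4: (3+2+1)/49 = 6/49 = 12.2%.

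**2. Dependence on the assumption (28-day pairs)**

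| Draw days | Fail as written | Fail with ±3 days |
|---|---|---|
| Uniform | 42.9% | 12.2% |
| Triangular | 41.4% | 5.9% |
| Day −3 to 0 only, uniform | 37.5% | 0% |
| Half exactly on day | 35.4% | 4.2% |
| 80% exactly on day | 17.7% | 0.7% |
| All on day | 0% | 0% |
| Dosing day and draw both uniform ±3 | 45.2% | 19.8% |

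**3. From Cycle 7, dosing on schedule**
- Next-cycle draw (nominal 21 days, range 15-27): 100% fail as written. With the tolerance a pass needs *d2* − *d1* ≥ 4, which is 6/49, so 43/49 = 87.8% still fail.
- Draw two cycles later (nominal 42 days, range 36-48): 0% fail.

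**4. Is a failed pair a lost event?** Take a rise at C3 and a C5 draw 27 days later.
- Last dose at C4: EOT is nominally 14 + 30 = 44 days after the rise. With the C3 dose 3 days late, the C3 draw 3 days after it, the C4 dose 3 days early and EOT 3 days early, it is 44 − 12 = 32 days, still at least 28.
- C5 dose given: it falls no earlier than day 27 − 3 = 24, so EOT is no earlier than day 24 + 27 = 51.

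Either way an EOT PSA taken in its window can confirm.

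**5. Where an event can be lost.** Take a rise drawn at the last dose, with EOT the only later PSA. Gap = 30 + *e* − *d*, both offsets uniform ±3.
- As written, the pair fails if *e* − *d* ≤ −3: (4+3+2+1)/49 = 10/49 = 20.4%.
- With the tolerance, it fails only if *e* − *d* = −6: 1/49 = 2.0%.
- If the rise is drawn exactly on the dosing day, only day 27 of days 27-33 fails: 1/7 = 14.3%.

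If EOT is brought forward before new therapy, the gap can be much shorter, and the tolerance rescues only gaps of 25-27 days.

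**6. Size of a delay.** If progression is dated at confirmation, waiting for the next scheduled draw adds nominally 28 days in the early cycles, or 42 − 21 = 21 days from Cycle 7. If it is dated at the first rise, a later confirmation does not move the event time.

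**The case against.** The strongest reply is that a failed pair is rarely a lost event. Section 6.1.5 asks for another PSA level, not the next one, and step 4 shows that an EOT value in its window normally satisfies the interval. Toxicity delays under Section 4.3 also carry forward without shortening the dosing interval, so they lengthen gaps, which a symmetric grid ignores. A PSA rise alone is not named among the stopping criteria in Section 4.5, so one cannot assume that patients with rising PSA stop at once. A stricter rule for progression than for response is not in itself a contradiction. All of this stands, and it limits the consequence.

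A reader might infer that about 4 in 10 PSA progressions go uncounted. The documents do not support that: 43% is a rate for pairs, covers only 28-day pairs through C7, and depends on the assumed draw days.

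A reader might also suppose that 10-30% of events become censorings and that, under a constant hazard, the median lengthens by a factor 1/(1 − *f*), that is by 11-43%. The arithmetic is right, but *f* follows from nothing in the schedule, and the censoring itself is inferred.

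The reply does not cover the last-dose case, an EOT visit brought forward, the 21-day draws from Cycle 7, or the missing dating rule.

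**Conclusion.** The concern holds with limited reach. The wording gap is certain: progression lacks the tolerance that CR and PR have, and the early schedule sits exactly on the minimum. The 43% rests on uniform, independent draw days and ranges from 0% to about 45% in the cases tried; the failure of on-schedule next-cycle draws from Cycle 7 needs no assumption about how draw days are distributed within the window.

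The usual result is delayed confirmation, which shifts event times only if progression is dated at confirmation. Loss of an event is mainly confined to a rise at the last dose with EOT under 28 days later (about 20% of such pairs under the same assumption) and to EOT brought forward before new therapy. The direction is toward longer time to PSA progression, but the amount cannot be derived from the documents. Only this secondary endpoint and the PSA stable/progression labels are affected; the PSA response rate and the Simon design are not.

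**What to change.** 1. In Section 6.1.5, add (±3 days) to the progression line, matching CR and PR.
2. State that any later PSA meeting the interval, including the EOT value, can confirm.
3. In Section 6.3.2, date progression at the first qualifying rise.
4. Reconcile the odd-cycle PSA schedule in Section 6.3.2 with the each-cycle schedule in the Cycle 7+ calendar.

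The cost is a few sentences in an amendment, with no new visit or blood draw. The tolerance is a partial remedy. Under the uniform assumption about 12% of 28-day pairs and 88% of 21-day next-cycle pairs would still need a later PSA, which is why items 2 and 3 matter. Most early EOT visits would remain unresolved, so the report should count patients whose last PSA was an unconfirmed rise.
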